6.7 Description of Investigational Agents

Brentuximab vedotin for Injection is a sterile, preservative-free, white to off-white lyophilized cake for reconstitution for IV administration. Brentuximab vedotin for Injection is supplied in single-use, Type 1 borosilicate glass vials with FluroTec®-coated butyl rubber stoppers and aluminum seals. Each vial of the product contains 50 mg of useable brentuximab vedotin, trehalose, sodium citrate, and polysorbate 80. The lyophilized product, after reconstitution with 10.5 mL sterile Water for Injection, USP, yields 11 mL of brentuximab vedotin solution (5 mg/mL concentration after reconstitution).

6.8 Preparation, Reconstitution and Dispensing

Brentuximab vedotin is an anticancer drug, and as with other potentially toxic compounds, caution should be exercised when handling brentuximab vedotin.

Recommended safety measures for handling and preparation include masks, protective clothing, gloves, and vertical laminar airflow safety cabinets.

Study treatment vials are single-use containers. Any partially used vials or diluted dosing solutions are to be discarded using appropriate institutional drug disposal procedures.

Study treatment must be reconstituted with the appropriate amount of sterile water for injection. GENTLY swirl the vial until the contents are completely dissolved. **The vial must not be shaken or vigorously swirled**; excess agitation may cause aggregate formation. Visually inspect the reconstituted drug product for any particulate matter and discoloration.

The appropriate amount of reconstituted study treatment will be withdrawn from the vial(s) and diluted in a 150 to 250 mL infusion bag containing 0.9% Sodium Chloride Injection, USP.

There are no known incompatibilities between study treatment and polypropylene (PP), polyvinyl chloride (PVC), ethyl vinyl acetate (EVA), polyolefin, or polyethylene (PE) bags. The bag should be gently inverted to mix the solution. **The bag must not be shaken**; excess agitation may cause aggregate formation. Prior to administration, the reconstituted and diluted drug product should be inspected visually for any particulate matter and discoloration.

The formulation contains no preservative and is intended for single use only; infusion solutions should be prepared and transferred using aseptic technique in a bio-safety hood.

6.9 Packaging and Labeling

Vials of study treatment will be packaged as one single-use vial per carton (kit). Vials and kits will be labeled to meet country-specific regulatory requirements.

6.10 Storage, Handling and Accountability

Vials containing brentuximab vedotin must be refrigerated at 2°C to 8°C in a secure location (e.g., locked room) accessible only to the pharmacist, the investigator, or a duly designated person.

Brentuximab vedotin does not contain preservatives; therefore, opened and reconstituted vials of study treatment must be used within 24 hours when stored under refrigeration at 2°C to 8°C. Reconstituted brentuximab vedotin should not be stored at room temperature. It is recommended that brentuximab vedotin vials and solutions be protected from direct sunlight until the time of use. **Reconstituted vials must not be shaken**.

A study drug accountability log must be completed for all brentuximab vedotin dispensed and administered to study patients.

6.11 Study Compliance

Study drug will be administered or dispensed only to eligible patients under the supervision of the investigator or identified sub-investigator(s). The appropriate study personnel will maintain records of study drug receipt and dispensing.

6.12 Termination of Treatment and/or Study Participation

Patients will be informed that they have the right to withdraw from the study at any time for any reason, without prejudice to their medical care. The investigator also has the right to withdraw patients from the study for any of the following reasons:

- Adverse event
- Protocol violation
- Lost to follow-up
- Progressive disease
- Study terminated
- Other

Patients who are withdrawn from the study will not be replaced.

At the time of withdrawal, all study procedures outlined for the End of Study visit should be completed. The primary reason for a patient's withdrawal from the study is to be recorded in the source documents and CRF.

7 STATISTICAL AND QUANTITATIVE ANALYSES

7.1 Statistical Methods

In general, summary tabulations will display the number of observations, mean, standard deviation, median, minimum, and maximum for continuous variables, and the number and percent per category for categorical data. Kaplan-Meier survival curves will be provided along with their 2-sided 95% CIs for time-to-event data.

7.1.1 Determination of Sample Size

Optimal Simon's two-stage design

- $\alpha=0.05$, $\beta=0.20$
- $P_0=0.20$, $P_1=0.45$
- Stage 1: 2/10 (≥ 3 responders are required to move to stage 2)
- Stage 2: 7/22 (8 or more responses are required to reject the null hypothesis)
- Total patients: $22 + 3$ (10% drop-out rate) = 25 patients

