4 STUDY DESIGN

4.1 Overview of Study Design

This is an open-label, non-randomized, multi-center, phase II trial of brentuximab vedotin to evaluate ORR primarily in patients with EBV- and CD30-positive lymphomas. The ORR will be evaluated based on the revised Cheson's criteria¹ or modified SWAT criteria² in case of cutaneous EBV- and CD30-positive lymphomas. Patients may receive up to 16 cycles of brentuximab vedotin.

Tumor measurements will be assessed (CT and PET scans) at screening, after completion of cycle 2 (Cycle 2 Day 21 ± 7 day), and at 4 to 8 weeks after the last dose of brentuximab vedotin. CT scans only will be used for the disease assessment follow-up every 3 months until the study closure.

Safety will be evaluated according to National Cancer Institute Common Terminology Criteria for Adverse Events (NCI CTCAE), Version 4.03, as well as by measuring changes from baseline in the patient's vital signs, ECOG performance status, electrocardiogram (ECG), and clinical laboratory results.

Patients may discontinue therapy at any time. Patients will attend the EOT visit 30 (± 7) days after completion of their last dose of brentuximab vedotin.

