4.2 Number of Patients

Based on the optimal Simon's two-stage design, at least 3 responders among stage 1 patients (N=10) are required to enter into a stage 2. The stage 2 will be delayed until the completion of ≥ 4 cycles of study medication in the last patient in stage 1, so-called interim analysis of stage 1. A total of 25 patients with EBV- and CD30-positive lymphomas will be enrolled.

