7.1.3 Populations for Analyses

The populations used for analysis will include the following:

Safety population: patients who receive at least 1 dose of study drug will be used for all safety analyses. All patients in the safety population will be analyzed according to the actual treatment received.

Intent-to-Treat (ITT) population: all patients randomized to treatment. All patients in the ITT population will be analyzed according to the treatment they were randomized to receive and not according to what they actually received, if different.

Per-Protocol (PP) population: a subset of ITT patients who do not have a major protocol violation as determined by the project clinician. All decisions to exclude patients from the PP population will be made prior to database lock.

Response-Evaluable population: all patients with diagnosis as confirmed by an independent pathology review facility, with measurable disease at baseline, who receive at least 1 dose of study drug, and have at least 1 postbaseline response assessment.

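### The final cut-off of 8 responses is calibrated to 22 analysed patients, but ORR is assigned to an ITT set that can only sensibly mean the 25 enrolled, and no cut-off is given for 23 to 25

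*Combined protocol and SAP*

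**What the plan says.** Section 7.1.1 specifies an optimal Simon two-stage design with alpha 0.05, beta 0.20, P0 = 0.20 and P1 = 0.45. The stage 1 rule is repeated in 4.2: "at least 3 responders among stage 1 patients (N=10) are required to enter into a stage 2". The final rule is "Stage 2: 7/22 (8 or more responses are required to reject the null hypothesis". The total is 22 plus 3: "10% drop-out rate) = 25 patients". Section 4.2 confirms the number: "A total of 25 patients with EBV- and CD30-positive lymphomas will be enrolled". Section 6.12 adds "Patients who are withdrawn from the study will not be replaced".

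Section 7.1.6 places efficacy evaluations on the ITT population by default, and names ORR as the primary efficacy analysis without naming another set. Section 7.1.3 defines that set as follows: "Intent-to-Treat (ITT) population: all patients randomized to treatment". Section 4.1, however, describes the trial thus: "This is an open-label, non-randomized, multi-center, phase II trial of brentuximab vedotin". Section 7.1.3 also defines a Response-Evaluable population. It needs a diagnosis confirmed by independent pathology review and measurable disease at baseline, and is limited to patients "who receive at least 1 dose of study drug, and have at least 1 postbaseline response assessment". Nothing assigns ORR to that set. Section 7.1.4 gives no rule for counting patients whose response was never assessed.

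**The concern.** A Simon cut-off holds for one final sample size. The plan derives its cut-off for 22, enrols 25 once stage 2 opens, replaces nobody, and names a set for ORR that, read sensibly, contains everyone enrolled. The word randomized in the ITT definition cannot apply here, and 7.1.6 itself dates OS from enrolment, so all enrolled is the natural reading.

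This is the only formal test of the primary endpoint. If 8 responses among 25 patients are declared a success, the decision uses a threshold that was not calibrated for 25. If the denominator or the cut-off is chosen after responses are known in an open-label trial, the stated error rates no longer describe the decision.

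**Working it through.** **Inputs.** P0 = 0.20, P1 = 0.45, alpha 0.05, beta 0.20, stop at 2 or fewer of 10, reject at 8 or more of 22, 25 enrolled (all from 7.1.1 and 4.2). Sidedness is not stated; Simon's design is one-sided. Planned drop-out is labelled 10%; the 3 added patients are 3/25 = 12%.

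**Formula.** With 10 patients in stage 1, n in total and cut-off c:

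P(reject | p) = sum over x = 3 to 10 of Bin(x; 10, p) × P[Bin(n − 10, p) ≥ c − x]

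**Step 1: reproduce the plan.** For n = 22, c = 8, p = 0.20, the terms are:
- x = 3: 0.2013 × 0.0726 = 0.0146
- x = 4: 0.0881 × 0.2054 = 0.0181
- x = 5: 0.0264 × 0.4417 = 0.0117
- x = 6: 0.0055 × 0.7251 = 0.0040
- x = 7 to 10 together: 0.0008

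The sum is 0.0492. The same sum at p = 0.45 gives power 0.8065. A full search confirms 2/10, 7/22 as the optimal design (expected size 13.87 under P0). The inflation also reproduces: 22/0.90 = 24.4, rounded up to 25.

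**Step 2: keep 8 or more, change the number analysed.**

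| n analysed | alpha (p = 0.20) | power (p = 0.45) |
|---|---|---|
| 22 | 0.0492 | 0.8065 |
| 23 | 0.0604 | 0.8332 |
| 24 | 0.0726 | 0.8531 |
| 25 | 0.0854 | 0.8675 |

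**Step 3: all 25 analysed, drop-outs counted as non-responders.** The plan does not state this rule; it is an assumption, with drop-out independent across patients and in both stages. Replace p by p(1 − d) and set n = 25. At d = 10%, for example, 0.20 becomes 0.18 and 0.45 becomes 0.405.

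| Drop-out d | 8 or more: alpha | 8 or more: power | 9 or more: alpha | 9 or more: power |
|---|---|---|---|---|
| 0 | 0.0854 | 0.8675 | 0.0401 | 0.8166 |
| 5% | 0.0669 | 0.8240 | 0.0298 | 0.7572 |
| 10% | 0.0512 | 0.7705 | 0.0215 | 0.6870 |
| 12% | 0.0457 | 0.7463 | 0.0188 | 0.6563 |

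Timing also matters. With exactly three losses and 8 or more required, alpha and power are 0.049 and 0.81 if all fall in stage 2, but 0.032 and 0.64 if all fall in stage 1.

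**Step 4: a rule that keeps the stated cut-off.** Test the first 22 assessable patients (all of them if fewer than 22) at 8 or more, with stage 1 the first 10 assessable. With m assessable of 25:

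P(reject) = sum over m of Bin(m; 25, 1 − d) × P(reject | n = min(m, 22))

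At n = 20 and 21, alpha is 0.030 and 0.039, so a shortfall never inflates alpha. At 10% drop-out, 22 or more are assessable with probability 1 − 0.236 = 0.764, and the average is alpha 0.046, power 0.79. At 12% it is alpha 0.043, power 0.78. This assumes that drop-out is unrelated to response.

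**The case against.** The strongest reply is that the cut-off was always meant for 22 evaluable patients. The 22 plus 3 arithmetic points that way, a Response-Evaluable set exists, and the comparative language in 7.1.6 (randomization date, stratified log-rank tests, hazard ratios) suggests wording written for a randomized trial. On that reading, with exactly 22 evaluable, the design delivers alpha 0.049 and power 0.81. This is a fair account of the likely intent, but the plan never assigns ORR to that set. It would not settle the matter either: once 25 are enrolled, 23 or more are assessable with probability 0.54 at 10% drop-out and 0.41 at 12%, and 8 responses is then too low a bar.

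A second reply is that a drop-out need not be a non-responder. Section 6.12 asks for End of Study procedures at withdrawal, and the schedule of events includes CT at that visit, so some withdrawn patients will have been assessed. This stands, and it makes the power figures conditional. It does not help alpha: more assessed patients move the denominator towards 25.

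Three stronger readings are tempting and not supported:
- That the sample size calculation is wrong. It reproduces exactly.
- That the trial runs at alpha 0.085 and power 0.75 at once. Alpha 0.085 requires no drop-out, where power is 0.87; power of 0.75 to 0.77 belongs to planned drop-out, where alpha is 0.046 to 0.051.
- That 25 patients cannot give power 0.80 under planned losses. With exactly three losses and 22 assessable patients tested at 8 or more, power is 0.81.

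**Conclusion.** The concern holds as a missing link between the cut-off and the analysis set, not as an error in the Simon design. On the set that 7.1.6 names, the stated threshold does not reliably deliver the stated error rates. Alpha exceeds 0.05 when losses fall clearly below plan, reaching 0.085 with none. At planned drop-out alpha is about right, and power is 0.77 (10%) or 0.75 (12%).

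The alpha figures by number analysed rest only on the plan's own rule and on reading ITT as all enrolled. The power shortfall rests further on counting drop-outs as non-responders, lost at random across both stages. It should be fixed before data are seen, since the correction is small and this is the primary test.

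**What to change.** In 7.1.3, define ITT as all enrolled patients. In 7.1.1 and 7.1.6, name one test set and its cut-off in advance, by one of two routes.

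**(a) Keep the stated cut-off.** Test the first 22 patients, in order of enrolment, who have measurable disease, at least one dose and a post-baseline response assessment. Stage 1 is the first 10 such patients. Losses are covered from the 3 allowance patients, so the total stays at 25, and 4.2 and 6.12 must say so. Require 8 or more, also if fewer than 22 are assessable. Report ORR in all 25 alongside, with unassessed patients as non-responders, because excluding them can bias ORR upward. State whether independent pathology confirmation is also required; exclusions on that ground are not in the drop-out allowance or in the averages above.

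**(b) Keep ITT.** Test all 25 enrolled, with stage 1 the first 10 enrolled and unassessed patients counted as non-responders. Require 9 or more (alpha at most 0.040), and restate power as 0.82 with no drop-out, 0.69 at 10% and 0.66 at 12%.

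The cost is a few sentences and no extra patients. Route (a) moves the formal test off ITT. Route (b) raises the bar by one response and states lower power. Route (a) retains more power and the stated threshold; route (b) stays closer to 7.1.6 as written.

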7.1.2 Randomization and Stratification

Not applicable

7.1.3 Populations for Analyses

The populations used for analysis will include the following:

Safety population: patients who receive at least 1 dose of study drug will be used for all safety analyses. All patients in the safety population will be analyzed according to the actual treatment received.

Intent-to-Treat (ITT) population: all patients randomized to treatment. All patients in the ITT population will be analyzed according to the treatment they were randomized to receive and not according to what they actually received, if different.

Per-Protocol (PP) population: a subset of ITT patients who do not have a major protocol violation as determined by the project clinician. All decisions to exclude patients from the PP population will be made prior to database lock.

Response-Evaluable population: all patients with diagnosis as confirmed by an independent pathology review facility, with measurable disease at baseline, who receive at least 1 dose of study drug, and have at least 1 postbaseline response assessment.

7.1.4 Procedures for handling Missing, Unused, and Spurious Data

All available efficacy and safety data will be included in data listings and tabulations. The relevance of missing sample data will be assessed. Data that are potentially spurious or erroneous will be examined according to standard data management operating procedures.

7.1.5 Demographic and Baseline Characteristics

Demographic and baseline characteristics will be summarized, including gender, age, weight, height, BSA, primary diagnosis, and other parameters as appropriate. No inferential statistics will be carried out.

7.1.6 Efficacy Analysis

All efficacy evaluations will be conducted using the ITT population unless otherwise specified. ORR will be used for the primary efficacy analysis using revised response criteria for malignant lymphoma (Appendix 12.3) or modified SWAT (Appendix 12.4) criteria. Duration of response in subjects with confirmed response is the time between first documentation of response and disease progression.

PFS and OS will be analyzed based on the ITT population using a stratified log-rank test. PFS is defined as the time from the date of randomization to the date of the first of (1) documentation of PD; (2) death due to any cause; (3) for patients who are confirmed non-complete responders, receipt of anticancer chemotherapy or radiotherapy for EBV- and CD30-positive lymphoma after completion of brentuximab vedotin. OS is defined as the time from the date of study enrollment to the date of death. Patients without documented death at the time of analysis will be censored at the date last known to be alive. Stratified log-rank testing will be used to compare OS between the groups. The hazard ratios along with the 95% CIs will be estimated using a stratified Cox regression model. The Kaplan-Meier method will be used to estimate the distribution of the OS endpoint. Median survival times (if estimable), along with the 2-sided 95% CIs will be presented. Analysis of OS will be performed based on the ITT population.

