SAEs	SAEs will be collected from signing of the main ICF through 30 days after the last dose of brentuximab vedotin.						
CTs of the neck, abdomen, and pelvis ^g	X		X	X		X	
Skin evaluation ^h	X		X	X		X	
PET/CT ⁱ	X		X				
Survival and disease status							X ^j

- a. All treated patients will be followed for PFS and OS status every 12 weeks (\pm 1 week) until the study closure. For patients who have progressive disease, survival/disease status and information regarding the initiation of an alternative lymphoma treatment may be obtained by phone call.
- b. Tumor tissue at any time will be collected (five unstained slides at 4 μ m thickness or a paraffin-embedded block) after the patient has signed the screening ICF. This will be used to assess CD30 status using Ber-H2 antibody (DAKO, Glostrup, Denmark) and biomarkers associated with sensitivity or resistance to brentuximab vedotin (eg, beta3- tubulin etc). Biomarker samples will be collected (EDTA 5mL x1 plus SST 3mL x1) to assess lymphocyte subsets and soluble CD30 quantification.
- c. The Cycle 1 Day 1 physical exam is not required if the screening physical examination was conducted within 7 days before administration of the first dose of brentuximab vedotin. A limited physical exam may be administered at the treating physician's discretion.
- d. A serum β -hCG pregnancy test will be performed for women of childbearing potential during screening. A negative urine pregnancy test is required if the serum pregnancy test was not done within 7 days of the first dose of study drug.
- e. Vital signs should be measured at screening and within 1 hour prior to infusion of brentuximab at day 1 of each cycle and EOT.
- f. A blood sample for hematology and serum chemistry including LDH will be obtained at screening and pre-dose at day 1 of each cycle and EOT. Hematology and chemistry blood samples for cycle 1, day 1 may be collected within 7 days prior to dosing to ensure patient eligibility on study day 1.
- g. Response to treatment and disease status assessments will be evaluated according to the Revised Response Criteria for Malignant Lymphomas¹ and the modified SWAT criteria.² MRI scans may be substituted for CT scans only if a patient 1) has a glomerular filtration rate of less than 60 mL/min such that IV contrast presents a risk of renal failure, 2) develops anaphylaxis to IV contrast, or 3) becomes pregnant during long-term follow-up. If use of MRI is required, a consistent scanning modality must be maintained.

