
During the treatment phase CT scans will be performed at:

- 1) Screening
- 2) CT scans of involved sites after cycle 2 of brentuximab every 6 weeks (window, \pm 7 days) until progressive disease or 16th cycle of brentuximab vedotin. After last dose of cycle 16: between 4 and 8 weeks following last dose of brentuximab. During the follow-up period: every 3 months until the study closure.
- h. In case of cutaneous lymphomas, total body skin scoring is calculated based on modified Severity Weighted Assessment Tool (mSWAT). This involves the direct assessment of the BSA of each type of skin lesions (palm plus fingers of the patient = approximately 1% BSA) in each of 12 areas of the body, multiplying the sum of the BSA of each lesion by a weighting factor (patch=1, plaque =2, and tumor = 3 or 4) and generating a sum of the subtotals of each lesions.
- i. This is mandatory at sites where a PET scanner is available. For all patients, if the screening FDG-PET scan is non-avid, the second interim FDG-PET scan will not be performed.
- j. Subjects will be followed for survival disease status every 3 months till the study closure.

TABLE OF CONTENTS

STUDY OVERVIEW DIAGRAM	5
SCHEDULE OF EVENTS	6
LIST OF TABLES	9
1 BACKGROUND AND STUDY RATIONALE.....	16
1.1 Scientific Background	16
1.1.1 Disease Under Treatment.....	16
1.1.2 Study Drug	16
1.2 Preclinical Experience.....	17
1.3 Pharmacology and Drug Metabolism in Humans	17
Pharmacokinetic properties	17
1.4 Clinical Experience	18
1.5 Study Rationale and Selection of Study Drug Doses.....	21
1.6 Potential Risks of brentuximab vedotin	22
2 STUDY OBJECTIVES	25
2.1 Primary Objectives.....	25
2.2 Secondary Objectives.....	25
2.3 Exploratory Objectives.....	25
3 STUDY ENDPOINTS	26
3.1 Primary Endpoints.....	26
3.2 Secondary Endpoints.....	26
3.3 Exploratory Endpoints	26
4 STUDY DESIGN.....	27
4.1 Overview of Study Design.....	27
4.2 Number of Patients.....	27
4.3 Duration of Study.....	27
5 STUDY POPULATION	28
5.1 Inclusion Criteria.....	28
5.2 Exclusion Criteria.....	29
6 STUDY DRUG	30
6.1 Brentuximab Vedotin Administration.....	30
6.2 Dose Modification Guidelines	31
6.3 Excluded Concomitant Medications and Procedures.....	32
6.4 Permitted Concomitant Medications and Procedures	33
6.5 Precautions and Restrictions	33
6.6 Management of Clinical Events	34
6.7 Description of Investigational Agents.....	37
6.8 Preparation, Reconstitution and Dispensing	38
6.9 Packaging and Labeling	38
6.10 Storage, Handling and Accountability	38

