some cases. (see section 4.4 of SmPC). Acute pancreatitis has been reported in patients treated with brentuximab vedotin and has contributed to fatal outcomes in some cases. Onset typically occurred after 1 to 2 doses of brentuximab vedotin. Early symptoms included severe abdominal pain, nausea, and vomiting. The estimated incidence of acute pancreatitis in patients treated with brentuximab vedotin is $\leq 0.5\%$. Approximately 1% of patients treated with brentuximab vedotin in the commercial or investigational setting have had an AE that was suggestive of a hepatobiliary disorder. The majority of events occurred after 1 to 2 treatment cycles and were characterized by asymptomatic mild to moderate transient elevation in aspartate aminotransferase and alanine aminotransferase. Elevated liver enzymes were observed upon rechallenge for some patients. Serious hepatobiliary disorders have been reported, but were confounded by comorbidities and/or concomitant medications with known hepatotoxic potential. Anaphylaxis has been reported outside of the pivotal phase 2 clinical trials discussed in this section. Symptoms of anaphylaxis may include, but are not limited to, urticaria, angioedema, hypotension and bronchospasm. Febrile neutropenia has been reported outside of the pivotal phase 2 clinical trials described in this section (see section 4.2). A patient enrolled in a phase 1 dose escalation trial experienced Grade 5 febrile neutropenia after receiving a single dose of 3.6 mg/kg of brentuximab vedotin.

Further details on these and other ongoing studies are provided in the Investigators Brochure (IB) and SmPC.

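### Duration of response ends only at progression, so a responder's death without documented progression is not an event, although the same death is a PFS event

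*Combined protocol and SAP*

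**What the plan says.** Section 7.1.6 defines DOR in one sentence: "Duration of response in subjects with confirmed response is the time between first documentation of response and disease progression". The paragraph that follows gives PFS three end events: documented progression, "death due to any cause", and, for confirmed non-complete responders only, "receipt of anticancer chemotherapy or radiotherapy for EBV- and CD30-positive lymphoma after completion of brentuximab vedotin".

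DOR is named as a secondary objective (protocol summary and section 2.2) and endpoint (section 3.2) but is not defined further there. The progression criteria in Appendices 12.3 and 12.4 rest on lesions and skin score; death is not progression under either. The one censoring sentence in 7.1.6 belongs to overall survival, and section 7.1.4 on missing data is general. For the analysis method, section 7.1 says "Kaplan-Meier survival curves will be provided along with their 2-sided 95% CIs for time-to-event data".

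The Schedule of Events sets the timing of disease assessment. On treatment, note g asks for "CT scans of involved sites after cycle 2 of brentuximab every 6 weeks", and afterwards "During the follow-up period: every 3 months until the study closure". Note a adds that "All treated patients will be followed for PFS and OS status every 12 weeks".

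**The concern.** A responder who dies before progression is documented has no DOR event under the stated definition. With Kaplan-Meier and no other rule, that patient would be censored. This is an inference from sections 7.1 and 7.1.6; the plan does not say it. Censoring assumes that the patient's later risk of progression equals that of responders still under observation, which has no meaning after death. The curve is then higher than the curve for time to progression or death.

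Such deaths are possible in this trial. On drug toxicity, section 1.4 states "Acute pancreatitis has been reported in patients treated with brentuximab vedotin and has contributed to fatal outcomes in some cases". Section 1.1.1 describes a disease with poor survival. A death can also fall between two scans, before progression is recorded.

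The two endpoints would also treat one death in two ways. In the same responders, the median DOR could exceed the median PFS although the DOR clock starts later. In a single-arm trial, durability is part of how the response rate will be read.

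**Working it through.** **The plan's own figures.** The documents state no figure for DOR. The design in section 7.1.1 reproduces: the rule 2/10 then 7/22 has exact type I error 0.0492 at P0 = 0.20 and power 0.8065 at P1 = 0.45, and 22/(1 − 0.10) rounds up to 25. DOR does not enter it, so nothing in the design changes.

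**Size of the DOR set.** At P1 = 0.45, 22 × 0.45 = 9.9 and 25 × 0.45 = 11.25 responders are expected. One death without progression is therefore about 10% of the set.

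**Analytic ratio (assumed constant hazards).** Let λ be the hazard of any response-ending event and f the share of those events that are deaths without progression. Counting death, the median is ln 2/λ. Censoring death, Kaplan-Meier estimates a curve with hazard (1 − f)λ and median ln 2/[(1 − f)λ]. The ratio is 1/(1 − f): 1.11 for f = 0.10, 1.25 for 0.20 and 1.43 for 0.30.

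**Hand check.** Take 11 responders with complete follow-up and ordered event times 1 to 11.
- Death counted: the curve is 6/11 = 0.545 after the 5th time and 5/11 = 0.455 after the 6th. The median is the 6th time.
- Events 2 and 4 are deaths and are censored: 10/11 × 8/9 × 6/7 × 5/6 = 0.577 after the 6th time, then × 4/5 = 0.462 after the 7th. The median moves to the 7th time.

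**Simulation (6,000 runs per case).**
- From the documents: 24 months of enrolment plus 6 months of follow-up; scans every 6 weeks to week 48 (16 cycles of 3 weeks), then every 12 weeks.
- Assumed: 11 responders, exponential DOR with true median (progression or death) of 9 months, first response at week 6, deaths on their own date, a 12-week enrolment pause after 10 patients.

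| Share f of deaths without progression | 10% | 20% | 30% |
|---|---|---|---|
| Reported median unchanged by censoring deaths | 77% | 57% | 38% |
| Median DOR above median PFS (or not reached against it), same responders | 18% | 36% | 53% |
| Median DOR not reached (about 4% if death counts) | 9% | 15% | 24% |

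When death counted in both endpoints, the median DOR never exceeded the median PFS in these runs. With true medians of 6 and 12 months, the second row becomes 17%, 34%, 50% and 17%, 34%, 49%. Leaving out the enrolment pause gives 76%, 57%, 40% for the first row. With exact progression dates and a 9-month true median, the typical median is 9.2 months with death counted, and 10.1, 11.3 and 13.0 months with death censored.

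**Sampling error.** The correctly defined median itself ranges over about 4 to 24 months (5th to 95th percentile).

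**Relapse after complete remission.** Appendix 12.3 puts relapse (after CR) and progression (after PR or SD) under one heading with shared criteria. Appendix 12.4 lists relapse in its own row, as any recurrence after complete response, while its progression row needs a set rise in skin score or new tumors. A small skin recurrence after complete response can thus be a relapse without being progression, and the DOR sentence names only progression.

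**The case against.** Time to progression among responders is a legitimate quantity and may have been chosen on purpose. Calling the other median the true one then assumes the answer. This is fair as far as it goes. But a progression-only measure needs a stated rule for deaths (censored at which date, or a competing risk), and the plan has none. The sentence needs an edit either way.

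The assumed shares have no support in the documents. Section 1.4 puts acute pancreatitis at no more than 0.5% and reports no febrile neutropenia in the pivotal studies, and section 6.6 reports no Grade 5 infections there. At shares of 1%, 2% and 5% the median is unchanged in about 97%, 96% and 87% of simulated trials. This stands as a caution on size. Those studies were in other lymphomas, however, and with 10 or 11 responders a single such death already makes about 10%.

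The comparison with PFS in the same responders is not a planned analysis, since PFS is analysed in the ITT population. A DOR longer than an all-patient PFS is no sign of error: the Hodgkin study in section 1.4 reports 6.7 and 5.6 months. This also stands. The comparison shows that the two definitions are inconsistent; it does not predict a line in the report.

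Section 4.1 lists fewer on-treatment assessments than note g (after cycle 2, then 4 to 8 weeks after the last dose), so the simulated scan schedule is one reading of the protocol. The relapse point is narrow and rests mainly on the skin criteria.

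**Conclusion.** The point holds. As written, DOR has no event for a responder who dies without documented progression, and the plan gives no other rule for that patient. If such deaths are censored, the reported DOR errs towards being too long. The ratio is about 1.11 to 1.43 for shares of 10% to 30%, under constant hazards and with all inputs assumed. In one trial of about 11 responders the median will often not move, and the bias is smaller than the sampling error; it does not average out, because it has one direction. The effect is confined to a secondary endpoint without a hypothesis test. The ORR test, the sample size, PFS and OS are unaffected. The change should be made, but it is not critical to the trial's main conclusion.

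**What to change.** Replace the DOR sentence in 7.1.6 with:

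> DOR runs from the first documented CR or PR to the earliest of disease progression, relapse after CR, or death from any cause; responders without an event are censored at their last disease assessment. New anticancer therapy before progression is handled in DOR as in the PFS definition.

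Under the second sentence, new therapy ends DOR for partial responders on the same terms as PFS. For complete responders it is not an event, and they are followed to relapse, progression or death. This wording drops the qualifier confirmed, which the plan does not define; it can stay if a definition is added.

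If a progression-only measure is wanted, it should be given a separate name and a stated rule for deaths.

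The cost is two sentences. No data are needed beyond those already collected for PFS and OS. The reported DOR may be shorter, and a death unrelated to lymphoma will count as the end of a response. Making the change before analysis avoids choosing a rule after seeing a handful of responders.
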